3.2. Innovation

The current proposal is the first targeted solution that seeks to reduce heart failure readmissions through improved sleep apnea treatment adherence by allowing patients to have ready access to at-home assistance with their PAP throughout the night. Furthermore, we propose to extend these successes in the proposed SBIR by adding several additional features.

Phase 1: We will develop new technology to incorporate real-time at-home pulse oximetry data. This will allow health care providers to have a highly relevant, non-invasive measure of sleep apnea efficacy that extends beyond currently limited options. In addition, we will use structured interviews to identify key areas for educational intervention and develop relevant educational material to embed within the AirCare system for patient access at home. Of particular importance to sleep apnea care, we will use the Phase 1 portion of the study to build in links to an on-call sleep technician. The Penn Sleep Center currently has eight sleep technicians working each night supervising sleep studies. The majority of their active duties occur from 6 PM to 9 PM as they connect patients to the in-lab sleep study equipment. After 9 PM until 6 AM the next morning, they are generally passively observing patients on the monitors or scoring sleep studies from the prior nights. This creates an available, trained sleep technician resource that could assist patients at home using the videoconferencing features of the AirCare Tablet from 9 PM to 6 AM. Since these staff are already working, they can provide assistance to patients affiliated with the sleep clinic without additional financial cost to the sleep clinic. Furthermore, since they are health care employees of the sleep clinic that also takes care of the patient, they are allowed to view patient healthcare data.

Phase II: We will further integrate the AirCare system with the PAP device internal adherence data, creating a directly linked comparison between PAP and a key outcome—nocturnal pulse oximetry. We will develop risk classification algorithms to interpret the real-time oximetry and PAP data and make it available to patients and providers through the AirCare system.

We will then test the AirCare system in a large demonstration randomized controlled trial. This will be the first randomized trial examining the impact of enhanced sleep apnea treatment on 30-day hospital readmission rates.

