Patients: We will conduct interviews with three patient groups at various points along the hospital timeline: 1) inpatients, 2) recently discharged patients and 3) patients at 4-6 months follow-up. We have elected to take this approach because the specific challenges a patient faces at each of these time points may differ, and if we wait until the end of the study to interview the patients, they may no longer recall the problems they faced earlier on, for example, during their hospital admission. We will interview at least 10 patients within each of these three groups. Eligible patients will be those admitted with a heart failure exacerbation diagnosis as their primary diagnosis or active heart failure during their hospital course that requires treatment modification. They must also be newly diagnosed with sleep apnea during their admission. The in-patient group will be approached shortly prior to their anticipated discharge date. The recently discharged patients will be interviewed 1-2 weeks post discharge, and the 4-6 month follow-up group will be contacted at 6 months for interviews.

Sleep Technicians: The Sleep Technicians will be responsible for providing overnight assistance to patients that are having difficulty using their PAP at home. The Penn Sleep Center employs over 30 sleep technicians that staff the 28 sleep study beds at 6 different locations. We will randomly invite them to participate and seek to conduct at least ten interviews using the framework described earlier.

Sleep medicine providers (physicians, nurse practitioners, nurses, medical assistants): The sleep medicine staff that provide day-to-day care for patients will be randomly selected for interviews, with at least 15 interviews, of which a minimum of seven will be with sleep medicine physicians.

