3.3.2.4 Task 2.4: Randomized Controlled Trial

The majority of effort during Phase 2 will be devoted to conducting a randomized controlled trial to assess the effectiveness of the AirCareLabs system for reducing 30-day readmission rates in a cohort of heart failure patients with sleep apnea. This study will be conducted at the University of Pennsylvania Health System under the guidance of [name] (sleep medicine), [name] (sleep medicine) and [name] (cardiology), with assistance from [name] and the AirCareLabs team. The proposed study flowchart is shown below.

3.3.2.5 Study Inclusion/Exclusion Criteria:

We have attempted to minimize the study inclusion/exclusion criteria in order to maximize study generalizability. Individuals must meet the following inclusion criteria prior to study enrollment: 1) Acute heart failure exacerbation requiring hospitalization (primary diagnosis) or admitted for another indication, but whose hospital course has become complicated by heart failure exacerbation. 2) Diagnosis of sleep apnea: Established by an apnea-hypopnea index (AHI) ≥ 5 events/hr consisting of predominantly obstructive apneas and hypopneas on full-night portable in-hospital polysomnography. This is the commonly used clinical criteria for sleep apnea in the setting of underlying cardiac disease (American Academy of Sleep Medicine 2005) (Gooneratne et al. 2012). 3) Age ≥ 18 years (see section on “Inclusion of Children”).

Individuals will be excluded from the study for the following reasons: 1) Inadequate sleep apnea treatment with PAP alone: (with up to 2 LPM oxygen) Unable to be adequately treated with PAP to a target AHI<15 events/hr and oxyhemoglobin desaturation nadir >90% and clinical improvement. 2) Unable to perform tests due to inability to communicate verbally, inability to write and read in English; less than a 5th grade reading level; visual, hearing or upper extremity motor deficit (e.g., previous stroke that prevents patient from using PAP treatment).

3.3.2.6 Subject recruitment:

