As part of their routine clinical care, patients with active heart failure exacerbation will be evaluated by the sleep in-patient consult service and undergo a portable sleep study. Those with newly diagnosed sleep apnea that elect to start PAP therapy and are adequately treated with PAP therapy will be eligible to participate in the Phase 2 clinical trial. They will undergo an informed consent session using an IRB-approved consent document. Based on our prior experience, we anticipate that approximately 75% will agree to participate. Thus to enroll 240 participants, we must approach 320 heart failure patients with diagnosed sleep apnea. Our preliminary data demonstrated that approximately 80% of admitted heart failure patients have sleep apnea, thus 400 heart failure patients will need to be screened for sleep apnea. The sleep disorders consult service has 10 new consults each week from the cardiology inpatient units for sleep apnea screening, thus approximately 500 new consults per year; we anticipate this volume will be adequate to enroll the required cohort for the Phase 2 study.

We will also recruit subjects from the Presbyterian and Pennsylvania Hospitals, following the same recruitment strategy. We will enroll subjects with a previous OSA diagnosis, who were previously unable to use CPAP. We will also submit a query to the Penn Data store, for de-identified data for the following: age, BMI, gender,

dx of hypertension and CHF, in an effort to expand our recruitment sources. We are also adding an additional recruitment site; Washington University at St. Louis, (WASU), site PI: [name]. This site will follow the same recruitment strategy as Presbyterian and Pennsylvania Hospitals.

3.3.2.7 Study Procedures:

After completing the informed consent process, study participants will complete the following study questionnaires (copies are provided in the Appendix): a) Self-Efficacy Measure for Sleep Apnea (Weaver et al. 2003), b) Self-Care of Heart Failure Index (Riegel et al. 2004), c) RAND Medical Outcomes Study Short Form (SF-36) (Ware et al. 1992), d) Epworth Sleepiness Scale (ESS) (Johns 1993). In addition, the medical chart will be abstracted by the study research coordinator to complete the Cumulative Illness Rating Scale (CIRS), gather demographic data, medications and other relevant covariates (Miller et al. 1992). They will then be randomized in a 1:1 ratio to either the AirCareSystems tablet or standard care as described below:

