AirCareSystems Group: Study participants in this arm will receive a tablet computer with a pre-installed AirCare application. The tablet will be locked to prevent other usage. All data from previous users will have been wiped from the tablet. The patient will be instructed in the use of the tablet, and will be encouraged to view the installed educational content created in Phase 1.

At the time of discharge, the study participants will leave the hospital with the PAP unit, the tablet computer and an iHealth oximeter. (In the event the patient is discharged before their PSG, they will use the Embletta at-home sleep device to determine eligibility). At home, they will be asked to complete daily, brief questionnaires about their symptoms. They can also use the tablet to submit queries to request assistance with their sleep apnea care. These queries will be answered during the daytime by the day shift sleep technicians or sleep medical assistants according to the standardized care pathways developed earlier. At night, they will be answered by the sleep technicians staffing the 6 active sleep labs (operating seven days a week on all days except national holidays). They will also use the iHealth oximeter on a nightly basis for the first week, then on an as-needed basis thereafter depending upon their symptoms or requests from care providers. It is anticipated that the average study participant will make 2-5 night-time assistance requests, and 3-7 daytime assistance requests. The Risk Classification criteria developed in Task 2.3 will be applied to identify study participants who are at high risk of non-adherence or readmission.

PAP adherence will also be tracked using the built-in device PAP units. Hospital readmissions, ER visits and other doctor visits will also be recorded.

At the end of the first month of treatment, study participants will be asked to return their tablet and iHealth oximeter. They will also be asked to complete the same battery of study survey instruments they completed at the initiation of the study protocol; this will be repeated at six-month follow-up as well.

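### An outside site (St. Louis) is added for recruitment only: the plan does not say who answers its patients' AirCare queries or on what data access, and neither the randomisation nor the primary test accounts for site.

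*Combined protocol and SAP*

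**What the plan says.** - **Location.** Section 3.3.2.4: "This study will be conducted at the University of Pennsylvania Health System". No other institution is named there.
- **Added site.** Section 3.3.2.6 adds Washington University at St. Louis and says of it only: "This site will follow the same recruitment strategy as Presbyterian and Pennsylvania Hospitals". Delivery of the intervention there is not mentioned.
- **Night support.** Section 3.3.2.7, AirCare arm: "At night, they will be answered by the sleep technicians staffing the 6 active sleep labs". Section 3.3.1.1 shows whose labs these are: "The Penn Sleep Center employs over 30 sleep technicians that staff the 28 sleep study beds at 6 different locations". Daytime queries go to day-shift sleep technicians or sleep medical assistants, with no institution given.
- **Data access.** Section 3.2 explains why the technicians may see patient data: "since they are health care employees of the sleep clinic that also takes care of the patient, they are allowed to view patient healthcare data". It describes their help, at no added cost, as being for patients affiliated with the sleep clinic.
- **Allocation.** Section 3.3.2.7: "They will then be randomized in a 1:1 ratio to either the AirCareSystems tablet or standard care". Stratification and blocking are not mentioned.
- **Primary test.** Section 3.3.2.8 compares the proportions of adherent patients with a chi-square test and no site term.

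**The concern.** Recruitment was widened to another institution without a matching change to the description of the intervention. A St. Louis investigator following the text would not know who answers a patient's night query. The only stated basis for a technician's access to the data does not, on its face, cover a patient treated elsewhere. If support at that site were improvised or thinner, the AirCare arm would not receive one uniform intervention and the adherence difference could be diluted.

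The statistical plan also takes no account of site. If adherence differs between St. Louis and the Penn hospitals for any reason, chance imbalance by site adds noise to the comparison. A small overall effect could not be traced to one site or the other by any planned analysis.

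**Working it through.** **1. The plan's own figure.** Inputs from 3.3.2.9: 30% versus 50% adherent, two-sided 0.05, power 80%.

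n per arm = [1.96·√(2p̄(1−p̄)) + 0.8416·√(p₁(1−p₁)+p₂(1−p₂))]² / (p₂−p₁)², with p̄ = 0.40

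= [1.96·√0.48 + 0.8416·√0.46]² / 0.04 = (1.358 + 0.571)² / 0.04 ≈ 93.

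This matches the stated 93. Raising it by 30% gives 93 × 1.3 = 121, against the stated 120. The sample size is not in dispute; it assumes the full 20-point gain across the AirCare arm.

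**2. Chance imbalance by site.** The documents give no St. Louis share, so s = 10% to 30% is an assumption. With 240 participants allocated 1:1 without stratification, the between-arm difference in St. Louis share has SD = √(4s(1−s)/240).

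| Assumed share | SD | 95% range |
|---|---|---|
| 10% | 0.039 | ±8 points |
| 20% | 0.052 | ±10 points |
| 30% | 0.059 | ±12 points |

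The resulting shift in the adherence difference is roughly the imbalance times the site difference in adherence. With a 10-point imbalance and an assumed 20-point site difference, it is 0.10 × 20 = 2 points, against a planned effect of 20.

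**3. Dilution, as a sensitivity only.** Both the share and the fraction of the gain lost at St. Louis are assumed. AirCare rate = 50% − 20 points × share × fraction lost. Power = Φ{[(p₂−p₁)√n − 1.96√(2p̄(1−p̄))] / √(p₁(1−p₁)+p₂(1−p₂))}.

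Worked case, 20% share and half the gain lost: 50 − 20 × 0.2 × 0.5 = 48%. At n = 93, (0.18 × 9.644 − 1.96·√0.4758)/√0.4596 = 0.566, so power is 71%. At n = 120 the same formula gives 82%.

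| Share, half the gain lost | AirCare rate | Power, 93 per arm | Power, 120 per arm |
|---|---|---|---|
| none | 50% | 80% | 89% |
| 10% | 49% | 76% | 86% |
| 20% | 48% | 71% | 82% |
| 30% | 47% | 67% | 78% |

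**4. What a site-stratified test would gain.** In a simulation with a 30% St. Louis share, the Cochran-Mantel-Haenszel test gave 1 to 3 points more power than the plain chi-square when adherence differed between sites by 20 to 30 points. It lost almost nothing when sites did not differ.

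**The case against.** A reader might infer that AirCare cannot be given in St. Louis. The documents do not support that. Section 3.1.6 describes a remote service by tablet and secure video, and Penn technicians could answer a St. Louis tablet as they answer one in Philadelphia. The tablet, education, oximeter and daily questionnaires can be supplied anywhere, and the staff calls in 3.3.2.2 can be made from anywhere. The data-access sentence in 3.2 is a rationale for using existing staff, not an exclusive rule. Participants also sign a consent document, which may cover access by study staff.

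A reader might also treat night help as the single essential component and assume that the whole gain is lost without it. On that assumption, power at 93 per arm would be 62% at a 20% share and 51% at 30%. The text does not go so far. Section 3.1.5 calls the lack of night help a serious gap, and 3.1.6 lists provider access first, followed by education, reminders and caregiver involvement. Section 3.3.2.7 expects more daytime requests (3 to 7) than night-time ones (2 to 5).

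Nor may one state that the sites differ: usual care at St. Louis is not described. A large St. Louis share is not implied either, since 3.3.2.6 expects about 500 Penn consults a year against 400 patients to be screened.

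Finally, unstratified 1:1 randomisation is valid, and the error rate of the test already allows for chance imbalance. Stratification would not repair dilution. Section 3.3.2.8 also allows a secondary covariance analysis if baseline variables differ.

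All of this stands, and it limits the point. It does not say who supports St. Louis patients, and the secondary analysis neither names site nor examines the effect by site.

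**Conclusion.** The point holds as a gap in specification together with a cheap improvement to the design. Sections 3.2, 3.3.2.4, 3.3.2.6 and 3.3.2.7 do not agree on where the study runs, and they do not say who answers St. Louis queries or under what data access. Allocation and primary test are silent on site.

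The statistical cost of that silence is modest: a 95% range of about ±8 to ±12 points in site share between arms, given an assumed share of 10% to 30% of 240, and no planned look at the effect by site. This is not a bias. The power losses are sensitivities under two assumed inputs, not forecasts. If attrition is low, the case of a 20% share with half the gain lost stays above 80%.

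**What to change.** - **3.3.2.7:** stratify the 1:1 randomisation by site (St. Louis versus the Penn hospitals), using permuted blocks.
- **3.3.2.8:** replace the plain chi-square with a Cochran-Mantel-Haenszel test stratified by site, and report the adherence difference for each site. The site-specific figures should be read as descriptive: a 20% share is 0.2 × 240 = 48 participants, or 24 per arm.
- **3.2, 3.3.2.4, 3.3.2.6 and 3.3.2.7:** reconcile these sections. Name the outside site as a place where the study is conducted, and state who answers its patients' day and night queries and on what data-access basis.

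The cost is a stratified allocation list and a few sentences of text. The power loss is negligible if the sites turn out alike. Allocation has to be stratified before patients are randomised; it cannot be done afterwards.

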3.3.2.8 Data Analysis

Descriptive Comparisons Between Intervention Groups at Baseline: Descriptive analyses will be performed in order to characterize the two study groups (AirCare and Standard Care) and to confirm that the randomization resulted in no clinically significant group differences at baseline in demographic, sleep, and other parameters. If the groups differ with regard to baseline variables and these variables are found to have significant associations with outcomes, secondary analysis of covariance will be used to investigate the degree to which estimated relative efficacy depends on these baseline differences.

Hypothesis: The AirCareLabs system will improve PAP adherence post-discharge relative to standard care. Statistical analysis method: PAP adherence will be defined as at least 4 hours of use per night on at least 70% of the study nights (thus, in a typical 30 day month, the study participant will have used it 21 nights for greater than 4 cumulative hours each night); this is consistent with Medicare PAP usage criteria. We will review the PAP adherence downloads, which provide an objective measure of adherence, to determine what percentage of patients in each study arm (AirCare vs. Standard Care) met the adherence criteria (i.e., a patient may be either adherent or non-adherent with PAP). We will utilize a chi-square frequency comparison for this primary analysis.

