We have conducted a preliminary analysis of the first 106 consecutive patients from the in-patient program. These 106 patients were on the Hospital of the University of Pennsylvania Cardiology units for congestive heart failure (87.4%, of which 53.3% had New York Heart Association Class 3 and 41.1% had Class 4 heart failure) or other cardiovascular conditions. Of these 106 patients, 81 (78%) were found to have sleep apnea on their diagnostic in-hospital sleep study; this is consistent with findings from other research that suggest a high prevalence of sleep apnea in heart failure patients (Javaheri et al. 1998) (Herrscher et al. 2011). Of these patients, 80% (65/81) had predominantly obstructive sleep apnea and 20% (16/81) had predominantly central sleep apnea. Patients were then started on PAP therapy the next night while in the hospital and continued on PAP therapy at home.

Readmission and Emergency Department visit rates were then monitored as the primary outcome; this occurred in 16.2% of patients within 30 days after discharge. Patients were divided into PAP full users (adherent >4 hours of use a night), partially PAP users (adherent 0 to 4 hours per night) and non-users. The readmission rates are shown in the related Figure. The most striking finding is that while 29-30% of the partial users and non-users were re-admitted within 30 days, none of the PAP full users were re-admitted ($p=0.025$). Also of note, only 34% of the discharged heart failure patients were full users of PAP—the majority of discharged patients were either non-users (30%) or partial-users (36%); this highlights the need to develop interventions to improve PAP

adherence. The manuscript related to these findings is accepted for publication in the Journal of Clinical Sleep Medicine pending revisions (peer-reviewed journal).

While these findings are provocative, it is important to highlight the numerous limitations of the above preliminary data. First, this is a naturalistic quasi-experimental study—the patients were not randomized to PAP or sham-PAP. Second, the study has a small sample size. Third, echocardiographic data and other biomarker data was not available to examine physiologic mechanisms. Fourth, follow-up readmission data and PAP adherence data was only available in 56 out of the 81 patients. Despite these limitations, we believe the above data suggests a possible role for sleep apnea treatment for reducing heart failure readmissions.

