3.3.2.1 Task 2.1: PAP device data

The PAP devices collect hours of use, estimates apnea-hypopnea index through flow monitoring, and mask leak data on a nightly basis. This data is transmitted wirelessly by modems attached to each unit that connect to the cellular phone network. The large majority of Durable Medical Equipment (DME) providers offer this service since the insurance companies generally require documentation of adherence during the first three months of use to justify continued insurance coverage. This data is stored in a central server maintained by each of the major PAP equipment manufacturers, and is shared with the patient's providers through a web portal data review system. The companies also deliver this data in .csv files on a daily or weekly basis to provider groups, such as the Veterans Affairs administration, large group practices such as the Penn Sleep Center or health systems. The general data format is one row per night of use. During Phase 2, we will integrate this data into the AirCareLabs workflow and make it available to patients and providers directly through the AirCare system. We have elected to perform this in Phase 2 instead of Phase 1 because there are already several commercial platforms that allow for patients and providers to view their PAP-device data, therefore this offers less of a competitive advantage than direct integration of oximetry data, which we have therefore prioritized to Phase 1.

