3.3.2.9 Sample Size Analysis

The study statistical power will be based on a two-sided Type 1 error rate of 0.05, and a Type 2 error rate of 0.20; these are commonly used criteria for study power calculations.

Hypothesis: We anticipate, based on our preliminary data, that 30% of patients will be fully adherent to PAP therapy (use >4 hours per night for >70% of the month). An improvement in adherence to 50% would represent a clinically meaningful change. Using a power analysis based on the chi-square frequency comparison, we anticipate that a sample size of 93 study participants per group will provide an adequate study power. We will increase this by 30% to factor in study attrition or loss to follow-up, thus a sample size of 120 would be adequate.

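### Does the primary adherence comparison need a written rule for patients and nights without PAP data?

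*Combined protocol and SAP*

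**What the plan says.** Section 3.3.2.8 defines adherence as "at least 4 hours of use per night on at least 70% of the study nights", illustrated as 21 nights of a 30-day month. The device downloads serve to "determine what percentage of patients in each study arm (AirCare vs. Standard Care) met the adherence criteria". Each patient is classed from the device download ("a patient may be either adherent or non-adherent with PAP"), and the arms are compared by chi-square. The hypothesis concerns use after discharge. The section does not define an analysis set, or say how to treat a patient with no download or a night with no transmitted record. No other section does so.

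Section 3.3.2.9 takes 30% versus 50% adherent, two-sided 0.05 and 80% power, reaches 93 per group, and continues: "We will increase this by 30% to factor in study attrition or loss to follow-up, thus a sample size of 120 would be adequate".

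Section 3.1.3 says of the in-patient series that "follow-up readmission data and PAP adherence data was only available in 56 out of the 81 patients". Section 3.3.2.1 says of modem transmission: "The large majority of Durable Medical Equipment (DME) providers offer this service". It adds that insurers generally require adherence records for the first three months.

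**The concern.** A plan that budgets for lost patients but does not say how the primary test treats them leaves a choice open. Counting them as non-adherent shrinks both proportions and the difference between them. Dropping them keeps the difference but gives up the full randomised comparison. If loss differs by arm, the two rules can give different verdicts on the same data, and a rule picked after seeing the counts by arm would be hard to defend.

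Loss is also foreseeable. In the in-patient series 25 of 81 patients (30.9%) lacked joint readmission and adherence data. Contact differs by arm too: AirCare patients have a tablet on which "they will be asked to complete daily, brief questionnaires about their symptoms", while standard-care patients seek help themselves.

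**Working it through.** **Inputs** (section 3.3.2.9): p1 = 0.30, p2 = 0.50, two-sided alpha 0.05, power 0.80, equal allocation, 120 per arm enrolled. The documents give no expected loss, so every loss rate L below is an assumption.

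**1. The plan's own figure.** Pooled-variance formula, no continuity correction, with p = (0.30 + 0.50)/2 = 0.40:

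n = [1.960·√(2·0.40·0.60) + 0.842·√(0.30·0.70 + 0.50·0.50)]² / 0.20² = 92.999, so 93 per arm. Then 93 × 1.30 = 120.9, stated as 120. Both agree with the plan.

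**2. Equal loss L in both arms.** Dropped: n = 120(1−L) at 0.30 versus 0.50. Counted non-adherent: n = 120 at 0.30(1−L) versus 0.50(1−L).

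| L | Power, dropped | Power, non-adherent |
|---|---|---|
| 0 | 89% | 89% |
| 10% | 86% | 83% |
| 14.7% | 84% | 80% |
| 20% | 81% | 76% |
| 22.5% | 80% | 74% |
| 30% | 76% | 68% |

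At 22.5% loss, 120 − 27 = 93 remain, which is the plan's evaluable number. At the in-patient series' 30.9%, power would be 75% (dropped) or 67% (non-adherent).

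**3. Unequal loss, invented counts** (chi-square without continuity correction):

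- Standard care 12 lost, 32 adherent; AirCare 24 lost, 45 adherent. Dropped: 32/108 v 45/96, p = 0.011. Non-adherent: 32/120 v 45/120, p = 0.072.
- Standard care 24 lost, 29 adherent; AirCare 12 lost, 45 adherent. Dropped: 29/96 v 45/108, p = 0.089. Non-adherent: 29/120 v 45/120, p = 0.025.

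So the verdict can reverse in either direction, but these tables were chosen to lie on either side of 0.05.

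**4. How often the rules disagree.** Simulation with true 30% versus 50%, 120 per arm, each patient lost at random and unrelated to adherence. The two rules differ on significance in about 3% of trials at 5% equal loss, 5% at 10% and 7% at 15%. With standard care losing 20% and AirCare 10%, they differ in 10%; with the reverse, in 27%.

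**5. Nights.** A patient with 20 qualifying nights and 3 untransmitted nights (a scenario) scores 20/30 = 66.7%, non-adherent, on a fixed 30-night denominator. On recorded nights the score is 20/27 = 74.1%, adherent. The 21-of-30 illustration favours the fixed denominator without settling the point.

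**6. Evidence that sounds relevant but is not.**

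- The mean stay of 13.0 days in section 3.3.3 is the index admission, which precedes the post-discharge window.
- The 90% in section 3.3.2.11 is a milestone for transfer to the AirCareLabs server. The endpoint comes from device downloads, which section 3.3.2.1 places on the manufacturers' servers.
- Of the readmission or emergency visit outcome, section 3.1.3 says "this occurred in 16.2% of patients within 30 days after discharge". An emergency visit need not cost a night, and no full PAP user in that series was readmitted. Hospital nights would therefore fall mostly on patients likely to miss the 70% threshold anyway.

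**The case for a change.** The strongest case for a change is that the rule governs the primary test, costs a few sentences to write, and loses credibility if chosen after the counts by arm are known. Neither rule is automatically safe. With true adherence of 30% in both arms and losses of 20% (standard care) and 10% (AirCare), the false-positive rate is 8% when lost patients count as non-adherent and loss is unrelated to adherence. It is 9% when they are dropped and all were truly non-adherent. At 30% and 10% these become 19% and 27%. Section 3.3.2.1 also describes the data as one row per night used, which does not separate an unused night from an untransmitted one.

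It stands that the rule is unwritten and that stating it early is good practice. The size of the problem does not stand. The inflated error rates need a loss imbalance that the documents do not suggest. The device records use, adherence is tracked in both arms (section 3.3.2.7), and tablet questionnaires are not the source of the endpoint. Insurers' demand for records over the first three months covers the 30-day window and makes absent downloads less likely. The two sections do not really conflict either: replacing lost patients implies excluding them, and referring to patients in each arm is ordinary wording, not a rival rule.

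**Conclusion.** The concern does not call for a change. It identifies a detail that analysts fill sensibly: patients compared as randomised, recorded zero use treated as non-use, patients without a download either excluded (as the sample-size section implies) or counted as non-adherent, and the other version shown as a check. No stated figure is wrong. Writing the rule down would record a choice without correcting one.

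On the reading implied by section 3.3.2.9, 120 per arm keeps 80% power up to 22.5% loss. The lower limit of 14.7% arises only under a rule the plan does not state, and it assumes that 30% and 50% are rates among patients with data. The series' adherence data covered 56 of 81 patients, so that assumption is plausible. Both limits assume equal loss, and the 22.5% also assumes loss unrelated to adherence.

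The judgement would weaken if loss approached the in-patient series' 30.9%, or differed clearly between arms. That series is a guide only: it counts patients lacking joint readmission and adherence data in routine care. Loss by arm would show in ordinary reporting of patient flow.
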